	
localized, low grade tumors deemed cured and not treated with systemic therapy.
 
16. Subjects with a condition requiring systemic treatment with either corticosteroids (> 10 mg daily prednisone equivalents) or other immunosuppressive medications within 14 days of study drug administration. Inhaled or topical steroids, and adrenal replacement doses > 10 mg daily prednisone equivalents are permitted in the absence of active autoimmune disease.

STATISTICAL CONSIDERATIONS	
The primary endpoint for the study is 1 year landmark PFS rate. The historical control with nivo/ipi from the Checkmate 067 study is a 1 year PFS rate of ~50% [1]. The target for this study is 75% (improvement by 25%), which is deemed a clinically meaning improvement. This will require a sample size of 23 for a one sided alpha of 0.05 and the power of 0.80. A simon two stage approach will be utilized. The study will be stopped if there 7 or few subjects out of 14 subjects progression free at 1 year. If the study meets criteria for continuation to the second stage, an additional 9 subjects will be enrolled. In the final analysis, the null hypothesis will be rejected (i.e., accept the alternative hypothesis of improved efficacy with nivolumab/ipilimumab plus cabozantinib) if 16 subjects or more are progression free at 1 year of the 23 total subjects. Assuming a dropout rate of 15% during the time of study, up to 27 subjects will be enrolled.

TOTAL NUMBER OF SUBJECTS	27 enrolled subjects (23 subjects required for primary endpoint analysis)
ESTIMATED ENROLLMENT PERIOD	Estimated 18 months
ESTIMATED STUDY DURATION	Estimated 42 months (2 years beyond last patient enrolled)

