11 STATISTICAL CONSIDERATIONS

Simon's Two-Stage Design will be used in hypothesis testing for the primary endpoint of a 1 year PFS rate. Based on the Checkmate 067 data [1], a 1 year PFS rate in the historical control is assumed to be 50% (H0: PFS rate=50%). In this trial, a target 1 year PFS rate will be 75% (improvement by 25%, H1: PFS rate \geq 75%), which is deemed a clinically meaningful improvement. This will require a sample size of 23 for a one sided alpha of 0.05 and the power of 0.80. In the futility stage with the first 14 subjects, the study will be stopped if there are 7 or fewer subjects progression free at 1 year. In the final analysis, the null hypothesis will be rejected if 16 subjects or more are progression free at 1 year of the 23 total subjects. Assuming a dropout rate of 15% during the time of study, up to 27 subjects will be enrolled.

In the event of unplanned interim analyses are needed due to slow accrual or any other reasons, we will use the curtailing based SCPRT approach for statistical analysis [36].

The PFS rate in the final analysis will be calculated and a 2-sided Clopper–Pearson 95% confidence interval (CI) will be calculated. PFS and OS will be analyzed using Kaplan–Meier product-limit estimates. Median PFS and OS and the cumulative probability of PFS and OS will be presented with two-sided 95% CI if estimable.

Remaining analyses will be descriptive and exploratory in nature. TMB will be evaluated as a continuous variable and dichotomous breakdowns including previously reported high vs low status using a 21 nonsynonymous variants/MB cutoff [37]. PD-L1 status will use high/low cutoffs of 1% and 5% positive IHC rates [1]. Other variables will be analyzed based on published data or optimization of cutoffs. Statistical comparisons will be performed with SAS/R and looking to determine associations with biomarkers and clinical outcomes.

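### Does the two-sided 95% interval undercut the one-sided 5% primary test at exactly 16 of 23?

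*Combined protocol and SAP*

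**What the plan says.** Section 11 (Statistical Considerations) sets up the primary test: "Simon's Two-Stage Design will be used in hypothesis testing for the primary endpoint of a 1 year PFS rate". The null rate is 50% and the target 75%. On size it says: "This will require a sample size of 23 for a one sided alpha of 0.05 and the power of 0.80". The study stops for futility if 7 or fewer of the first 14 subjects are progression free at 1 year. At the end, "the null hypothesis will be rejected if 16 subjects or more are progression free at 1 year of the 23 total subjects". The Synopsis repeats the cut-off ("if 16 subjects or more are progression free at 1 year of the 23 total subjects") and adds that reaching it means accepting the alternative of improved efficacy.

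Estimation comes in a separate paragraph of section 11. For the final PFS rate, "a 2-sided Clopper–Pearson 95% confidence interval (CI) will be calculated". The Kaplan-Meier summaries use the same level: medians and the "cumulative probability of PFS and OS will be presented with two-sided 95% CI if estimable". The section plans no 90% interval and no one-sided bound, and it does not discuss how the interval relates to the test.

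**The concern.** A two-sided 95% Clopper-Pearson interval excludes 50% from below only when the one-sided exact p-value is under 0.025. The count rule needs only a p-value under 0.05. A result between those limits is declared positive while its interval still contains the null value.

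That gap falls on the smallest winning count, which is a plausible outcome. A report at 16/23 would say that 50% is rejected and print an interval starting at 47.1% beside it. In a single-arm trial against a fixed benchmark, many readers look first at whether the interval clears the benchmark, and some would take the result as not significant. Anyone who used the interval as the criterion would in effect be asking for 17/23. If the team chose a 90% interval only after seeing 16/23, the choice would look driven by the data.

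**Working it through.** **Inputs (section 11).** Null rate 0.50; target 0.75; stage 1 has 14 subjects and continues with 8 or more progression free; total 23, so stage 2 has 9; reject at 16 or more; two-sided 95% Clopper-Pearson interval. All figures assume exactly 23 analysed subjects.

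**1. The plan's own design.** With X1 ~ Bin(14, p) and X2 ~ Bin(9, p),

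P(reject) = Σ (x = 8 to 14) P(X1 = x) · P(X2 ≥ 16 − x).

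- p = 0.50: 0.0462, below 0.05.
- p = 0.75: 0.8016, above 0.80.
- With a cut-off of 15, p = 0.50 gives 0.1006, so 16 is the smallest cut-off that holds the level.

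The stated design reproduces.

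**2. Intervals around the cut-off.** For x of 23 at level 1 − α, the lower limit is the α/2 quantile of Beta(x, 24 − x). The upper limit is the 1 − α/2 quantile of Beta(x + 1, 23 − x). The p-value is P(Bin(23, 0.5) ≥ x), ignoring stage 1.

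| Count | Rate | One-sided p | Count rule | 95% interval | 90% interval |
|---|---|---|---|---|---|
| 15 | 65.2% | 0.1050 | not rejected | 42.7% to 83.6% | 46.0% to 81.4% |
| 16 | 69.6% | 0.0466 | rejected | 47.1% to 86.8% | 50.4% to 84.8% |
| 17 | 73.9% | 0.0173 | rejected | 51.6% to 89.8% | 54.9% to 88.0% |

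Only 16 has a p-value between 0.025 and 0.05. Test and 95% interval therefore agree at 15 and below and at 17 and above. The 90% interval agrees with the rule on both sides of the cut-off.

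**3. Allowing for the two stages.** Solving P(reject at 16 or more) = 0.025 for p gives a lower limit of 47.12%, against 47.08% unadjusted. At 0.05 it gives 50.40% against 50.36%. The mismatch comes from 2.5% versus 5% in the tail, not from ignoring the interim look.

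**4. How often it happens.** P(continue and total = 16) = Σ (x = 8 to 14) P(X1 = x) · P(X2 = 16 − x).

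- p = 0.50: 0.029
- p = 0.65: 0.158
- p = 0.70: 0.176
- p = 0.75: 0.148, which is 0.1479 / 0.8016 = 18.4% of successful trials at the target rate

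**5. The other planned interval for this rate.** Read at 1 year, the Kaplan-Meier cumulative PFS is a second estimate of the same quantity. With no censoring before 1 year (an assumption), S = 16/23 = 0.696 and the Greenwood standard error is √(0.696 × 0.304 / 23) = 0.096. The plan does not name a transformation.

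- Untransformed: 0.696 ± 1.96 × 0.096, or 50.8% to 88.4%, which excludes 50%.
- Log-log: S raised to the power exp(±1.96 × 0.380), where 0.380 = √(0.304 / (0.696 × 23)) / |ln 0.696|. This gives 46.6% to 84.2%, which includes 50%.

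So a matching 90% Clopper-Pearson interval would not ensure that every printed interval clears 50% at 16/23.

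**The case for a change.** The best case for a change is that it costs almost nothing. A few sentences could say that the count rule governs, attach a 90% interval to the test and label the 95% interval descriptive. The discordant count is the minimum success result. Its share of positive trials grows as the benefit shrinks: 18% at a true rate of 75%, 29% at 70% (0.1757 / 0.6156) and 38% at 65% (0.1579 / 0.4113). Fixing the level in advance also removes any suspicion of a choice made after the result.

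The arithmetic stands, and so does the point that the 90% interval is the one dual to a one-sided 5% test. The rest is weaker.

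- The plan already says how to read 16/23. Both section 11 and the Synopsis call it a rejection.
- Requiring 17/23 would give power 0.654 at the target rate. That is a property of a rule the plan does not contain, so it is not a power loss here.
- A one-sided test and a two-sided estimation interval answer different questions and need not be dual. Using 95% throughout the section is a coherent convention.
- The addition would keep the interval said to confuse readers and place another beside it.
- At 16/23 the 90% lower limit clears 50% by only 0.4 points. One can reasonably hold that the wider interval shows the uncertainty of a 23-patient study more candidly.

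**Conclusion.** The mismatch is real but confined to one count, and it affects presentation only. At exactly 16/23, with 23 analysed subjects, the count rule rejects 50% while the 95% Clopper-Pearson interval of 47.1% to 86.8% includes it. The chance of that is 0.148 at a true rate of 75% and 0.029 at 50%. Followed as written, the plan yields a valid decision with type I error 0.0462 and power 0.8016, and a valid 95% interval. A 90% interval alters neither, and whether to show one is a matter of preference. An analyst who meets 16/23 can report the rejection by the stated rule and note that the interval has 2.5% per tail. A sentence calling the 95% interval descriptive and naming the 90% interval (50.4% to 84.8% at 16/23) as the counterpart of the test would be harmless, but it is not needed. If the number analysed is not 23, the cut-off and these figures no longer apply as given.

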7.5 Treatment Response Assessment

Only those subjects who have measurable disease present at baseline, have received at least one dose nivolumab, ipilimumab and cabozantinib, and had one on-treatment scan or progressed clinically will be considered evaluable for response. These subjects will have their response classified according to the definitions stated below. Those subjects that are not evaluable for response will be replaced. Immune-Modified Response Evaluation Criteria in Solid Tumors (imRECIST) will be used for the primary response assessment and for progression free survival determination [33]. Best overall response rate will be reported. Start of treatment will define the start date for calculations of PFS and OS.

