7.6 Correlative studies

7.6.1 Biomarkers

A variety of factors impact the immunomodulatory properties and efficacy of immune checkpoint therapy, including nivolumab and ipilimumab, in patients with advanced melanoma. Baseline variables and changes that occur during treatment can be used to predict anti-tumor immune responses and to correlate with mechanisms of action of agents with immune modulatory properties, such as the RTK inhibitor cabozantinib. These include tumor specific factors such as tumor mutational burden, PD-L1 expression, MHC antigen presentation, interferon gamma related gene expression profiles [2, 34]. Host factors such as baseline peripheral lymphocyte counts, inhibitor immune cell levels (such as Tregs), HLA variants and dynamic changes during treatment have also been associated with responses to immune checkpoint therapy responses. Recent data on the gut microbiome indicates this may play a large

role in anti-tumor immunity as well [35]. In addition, anti-VEGF/R and anti-c-MET therapies have the ability to enhance T-cell priming and dendritic cell maturation, increase MHC antigen presentation on tumor cells, reduce immune suppressive Treg and myeloid cell populations, and activate vessel endothelium that can lead to augmented CD8+ T-cell and macrophage cell infiltration [4-8, 10, 11].

Assessment of baseline and on treatment molecular and cellular variables will serve the purpose of establishing predictive biomarkers for nivolumab/ipilimumab plus cabozantinib in patients with advanced melanoma. Exploratory analyses and comparisons to efficacy endpoints – ORR, PFS, and OS will be performed. In particular, this data will allow identification of sub-populations where clinical benefit is most often observed. We hope to show that patients typically predicted to have a low probability of response (e.g. PD-L1 IHC <1%, interferon gamma GEP low) will have substantial clinical benefit with the immunotherapy strategy investigated in this protocol. This will lead to future studies of nivolumab/ipilimumab plus cabozantinib in biomarker selected advanced melanoma patients.

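### Section 11 allows cut-offs for markers other than PD-L1 and the named TMB value to be optimised on at most 23 to 27 subjects without correction, while Section 7.6.1 aims to establish predictive biomarkers from a single arm

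*Combined protocol and SAP*

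**What the plan says.** Section 11 treats the markers in three ways.

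- **PD-L1** has two fixed thresholds: "PD-L1 status will use high/low cutoffs of 1% and 5% positive IHC rates".
- **TMB** is analysed as continuous and also split, with "dichotomous breakdowns including previously reported high vs low status using a 21 nonsynonymous variants/MB cutoff". The wording leaves room for other TMB splits.
- **Everything else** falls under one sentence: "Other variables will be analyzed based on published data or optimization of cutoffs".

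Testing follows: "Statistical comparisons will be performed with SAS/R and looking to determine associations with biomarkers and clinical outcomes". The paragraph opens with "Remaining analyses will be descriptive and exploratory in nature". Neither Section 11 nor any other section gives a significance level, a test, a range of candidate cut-points, an adjustment for the search, a resampling step or a validation step for these markers.

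Section 7.6.1 also calls the analyses exploratory and compares them with ORR, PFS and OS. It then says that assessing baseline and on-treatment variables "will serve the purpose of establishing predictive biomarkers for nivolumab/ipilimumab plus cabozantinib". After expressing the hope that PD-L1-low or interferon-gamma-low patients will benefit, it adds: "This will lead to future studies of nivolumab/ipilimumab plus cabozantinib in biomarker selected advanced melanoma patients".

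Hypothesis 2 in Section 2.0 concerns patients with low PD-L1 and low interferon-gamma scores, particularly those with high TMB. Section 11 gives no cut-off for the interferon-gamma score.

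**The concern.** Choosing the split that best separates outcomes, and then testing that split on the same data as if it had been fixed beforehand, is not a valid test. The p-value is the smallest of many, and the effect is the largest of many. An exploratory label lowers the claim made for the result, but it does not make that p-value or effect interpretable.

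The problem reaches a hypothesis the protocol names. The interferon-gamma-low group could be defined after outcomes are seen. The same rule covers the angiogenesis and RNA profiles, immune-cell measures, cytokines and microbiome in Sections 4.0 and 7.6.1.

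The stated purpose is a second problem. With every subject on the same regimen, a marker that identifies benefit from the combination looks the same as one that identifies patients who do well on any treatment. If the next study's population were chosen on such a result, it could rest on chance or on prognosis alone.

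**Working it through.** **Inputs from the documents.** Section 11 gives N = 23 (14 then 9), rejection at 16 or more of 23, 1-year PFS of 50% under the null and 75% as target, and up to 27 enrolled. The synopsis gives 18 months of accrual and 42 months in total, so follow-up runs from 2 to 3.5 years. Section 5.3 allows waivers of baseline tissue, so the number with tumour markers may be lower.

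**The plan's own figures first.** The plan states no error rate for the biomarker analyses. For the primary design, the exact two-stage binomial sum is the sum over x = 8 to 14 of P(X1 = x) × P(X2 ≥ 16 − x), with X1 binomial on 14 and X2 binomial on 9. It gives 0.0462 at a rate of 0.50 and 0.8016 at 0.75. This agrees with the stated one-sided 0.05 and power 0.80. For enrolment, 23/0.85 = 27.06, against 27 stated. The range of 23 to 27 is therefore a fair upper bound for the marker analyses.

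**Assumptions the documents do not supply.** These are a two-sided nominal 0.05, the test and the search window. Ranges are shown for the last two.

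**Method.** Simulate a continuous marker independent of outcome. For each admissible cut-point c in the window compute p(c), then take p_min = min p(c) and count a false positive when p_min is at or below 0.05. PFS is exponential with 50% or 75% at 1 year, followed to 1 year or for 2 to 3.5 years (6,000 runs per setting). Binary outcomes have a rate of 50%, 60% or 75% (10,000 runs per setting).

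In the binary-outcome runs at n = 23, a 20% to 80% window requires at least 5 subjects on each side (0.20 × 23 = 4.6, rounded up). Group sizes then run from 5 to 18, which is 14 cut-points. Fourteen independent tests would give 1 − 0.95^14 = 51%. Neighbouring cut-points share most subjects, so the true rate is lower.

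**False-positive rate per marker, n = 23 to 27:**

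| Search window | Log-rank (PFS) | Chi-square (binary) | Fisher (binary) |
|---|---|---|---|
| 33% to 67% | 17%–19% | 16%–20% | 9%–13% |
| 25% to 75% | 22%–26% | 20%–25% | 12%–16% |
| 20% to 80% | 25%–30% | 24%–27% | 14%–17% |
| 10% to 90% | 32%–42% | 29%–36% | 16%–22% |
| Fixed median split | 4.5%–5.8% | 4.4%–5.3% | 2.5%–3.9% |

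A separate simulation agreed to within about a percentage point and put the upper ends at 43% (log-rank) and 23% (Fisher). At n = 20, which waivers could produce, the ranges are 16% to 45% (log-rank) and 8% to 16% (Fisher).

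The last row shows that the search is the cause: at the same sample sizes, a split fixed in advance holds about 5% or less.

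**The case against.** The strongest reply is that these are exploratory analyses, labelled so in the objectives, in Section 7.6.1 and in Section 11. No primary, secondary, futility or safety decision depends on them. PD-L1 and one TMB cut-off are already fixed, and published cut-offs are an allowed alternative to optimisation for the rest. The plan is silent on adjustment; it does not say that p-values will be reported unadjusted. All of this stands. It limits the scope and weight of the point, but it leaves a named method with no safeguard and a purpose stated more strongly than the label allows.

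A reader might also infer more than the documents support:

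- **A fixed error rate such as 17% to 30% per marker.** The plan states no level, test or window, so any rate is conditional.
- **A near-certain false finding across markers.** With five independent markers at 17% to 30% each, 1 − 0.83^5 = 61% and 1 − 0.70^5 = 83%. This is only an illustration: the plan does not say that five markers will be optimised, and correlated markers would give less.
- **An optimised split that will select the next trial's population.** The sentence on future studies follows a stated hope, and its PD-L1 example uses a fixed cut-off. No rule ties an optimised split to selection.
- **A planned immortal-time bias.** Section 7.5 says "Start of treatment will define the start date for calculations of PFS and OS", and Section 7.6.1 mentions on-treatment variables beside efficacy comparisons. But Section 4.0 ties ORR, PFS and OS to baseline tumours, and ties the on-treatment biopsy to change from baseline. The documents permit a comparison of on-treatment markers with PFS or OS but do not prescribe one.

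**Conclusion.** The point holds for markers other than PD-L1 and the named TMB cut-off, where the optimisation route is used. At n = 23 to 27 and an assumed two-sided 0.05, the null false-positive rate per marker is about 9% to 43% depending on test and window. Every setting tried was well above the rate for a fixed split. The direction of the bias in the effect is certain (overstatement), but its size was not computed.

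Separately, and without any calculation, Section 7.6.1 sets a purpose that a single-arm trial cannot meet, and that purpose conflicts with the exploratory label in Section 11.

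The primary analysis is untouched. The change should be made before the marker data are analysed, but it is not a barrier to the trial.

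**What to change.** In Section 11, replace the optimisation wording with text along these lines: each marker is analysed as continuous, or at a published or median cut-off fixed before outcomes are examined; the interferon-gamma score cut-off is named now. Any data-driven cut-off is reported only with a permutation-adjusted p-value for the maximally selected statistic and a bootstrap-corrected effect estimate, with the search range stated.

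In Section 7.6.1, describe the results as hypothesis-generating associations with outcome that cannot separate predictive from prognostic effects.

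If on-treatment markers are to be compared with PFS or OS, add that time starts at the sampling visit, among subjects still at risk then.

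The cost is a few lines of text and a little programming, with no change to visits, samples or sample size. The downside is fewer nominally significant exploratory results.

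### Section 11 lets marker cutoffs be optimised in the trial's own data before comparison with outcome, with no search range, selection adjustment or validation

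*Combined protocol and SAP*

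**What the plan says.** Section 11 opens its last paragraph with "Remaining analyses will be descriptive and exploratory in nature". It then sets out three rules for cutoffs:

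- **TMB:** analysed as continuous and in dichotomies, including "previously reported high vs low status using a 21 nonsynonymous variants/MB cutoff".
- **PD-L1:** "PD-L1 status will use high/low cutoffs of 1% and 5% positive IHC rates".
- **Everything else:** "Other variables will be analyzed based on published data or optimization of cutoffs".

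The next sentence is "Statistical comparisons will be performed with SAS/R and looking to determine associations with biomarkers and clinical outcomes". Section 7.6.1 names ORR, PFS and OS as the efficacy endpoints for these comparisons. It gives the results a purpose: "this data will allow identification of sub-populations where clinical benefit is most often observed", and "This will lead to future studies of nivolumab/ipilimumab plus cabozantinib in biomarker selected advanced melanoma patients".

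The third rule could cover several markers. The second hypothesis in Section 2.0 and the text of Section 7.6.1 both rely on a low interferon gamma expression score, but no section defines low. Section 7.6.1 also lists blood immune cell populations, cytokines and the stool microbiome.

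**The concern.** The p-value of a log-rank or Fisher test is calibrated for a split chosen without sight of outcome. Optimisation, in its usual sense, picks the split that separates outcomes best. The ordinary p-value then describes that one split as if it were the only candidate. It no longer tests whether the marker is related to outcome. The high/low estimate is biased away from no effect for the same reason.

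What is at stake is the choice of sub-populations and of later marker-selected studies, which Section 7.6.1 says these results will inform. The bias is worst in small samples, and this trial has at most 27 patients.

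**Working it through.** **Plan's own figure.** The documents give no error rate for the biomarker analyses. The sample size of 23 does reproduce. With 14 + 9 patients, stopping at 7 or fewer of 14 and rejecting at 16 or more of 23, exact binomial sums give a one-sided alpha of 0.0462 at a rate of 50% and a power of 0.8016 at 75%.

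**Inputs from the documents.** N = 23 evaluable and up to 27 enrolled (Section 11). 1-year PFS of 50% (null) or 75% (target) (Section 11). Enrolment of 18 months and total duration of 42 months (Synopsis), so follow-up runs from 2 to 3.5 years.

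**Assumptions, because the plan is silent.** Exponential PFS, S(t) = p^t with t in years. Censoring uniform on 2-3.5 years. One continuous marker independent of outcome. Every cutoff in a central range tried. Two-sided 5% level with no adjustment.

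**Method.** For each cutoff k, the log-rank statistic is Z²(k) = U(k)²/V(k). U is the sum over events of (high-group indicator minus the high-group share at risk), and V is the sum of share × (1 − share). A trial counts as a false positive if the largest Z²(k) exceeds 3.84. For a binary outcome, the smallest Fisher p-value over k is compared with 0.05.

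**Rough check on size.** At N = 23 the central 60% runs from 4.6 to 18.4, so k = 5 to 18, which is 14 splits. If these were independent, the false-positive rate would be 1 − 0.95^14 = 51%. Neighbouring splits share most patients, so the true rate must be lower. Simulation gives about 30%.

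**Results: false-positive rate for one unrelated marker.** Log-rank used 10,000 runs (3,000 for the central third). Fisher used 3,000 runs.

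| N, 1-year rate | Test | Central 80% | Central 60% | Central 50% | Central third |
|---|---|---|---|---|---|
| 23, 50% | log-rank | 39.5% | 30.0% | 25.8% | 18.5% |
| 23, 75% | log-rank | 35.4% | 27.2% | 24.2% | 17.3% |
| 27, 50% | log-rank | 41.7% | 28.4% | 25.9% | 17.8% |
| 27, 75% | log-rank | 38.1% | 27.5% | 24.4% | 18.8% |
| 23, 50% | Fisher | 19.9% | 16.0% | 13.8% | 11.8% |
| 23, 75% | Fisher | 16.3% | 13.5% | 12.4% | 10.4% |
| 27, 50% | Fisher | 22.2% | 16.8% | 16.2% | 12.9% |
| 27, 75% | Fisher | 18.1% | 13.8% | 14.2% | 10.4% |

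Repeat simulations reached about 43% for log-rank and 24% for Fisher. A fixed median split gives about 5%-7% with log-rank and 2%-4% with Fisher, so the excess comes from the search.

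**Exaggeration.** At N = 23, with a 50% 1-year rate and a central 60% search, the falsely significant log-rank results have a median one-step hazard ratio of about 4, where the true value is 1.

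**Effect of adjusting.** If the best log-rank statistic is referred to its own null distribution, the rate returns to 4.0%-5.5% in held-out runs. For N = 23-27 the best cutoff then needs an unadjusted p of about 0.001 (central 80%), 0.003-0.005 (central 60%) or 0.004-0.006 (central 50%). In 2,000 further trials at N = 23 (central 60%), the uncorrected search rejected 28.7%, a permutation test of the maximum 4.5%, and a test of the marker as continuous 5.8%.

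**The case against.** The strongest reply is that the paragraph declares these analyses descriptive and exploratory, assigns them no alpha and names no test. On that view, comparison with 5% holds the plan to a standard it never set. The rule also offers published cutoffs as an alternative, so nothing shows that a given marker will be optimised. A later marker-selected study would test the marker afresh.

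Much of this stands, and it limits what can be claimed:

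- A reader might infer that optimised cutoffs will be tested as though fixed in advance. The plan does not say so. It is silent on adjustment, which permits that practice without prescribing it.
- A reader might take the log-rank range as the plan's error rate. It depends on a test and search range that the documents do not give. Fisher on response or 1-year status gives clearly less.
- A reader might conclude that unrelated markers will be reported as associated. Even at 24%-43%, 57%-76% of searches on an unrelated marker find nothing.
- Not all biomarkers are involved. PD-L1 and the named TMB cutoff are prespecified, and the on-treatment biopsy endpoint in Section 4.0 is a change from baseline that needs no cutoff.
- Tissue analyses may have fewer than 23 patients, because Section 5.3 allows a waiver of baseline tissue and makes later biopsies optional. With 14 patients the rates are 21%-40% for log-rank (central 50% to central 80%) and only 5%-9% for Fisher.
- False positives accumulated over several markers are a separate multiplicity question, which a search adjustment would not solve.

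The exploratory label excuses the absence of formal error control across markers. It does not make a p-value or an effect estimate correct after the cutoff was chosen to maximise it, and Section 7.6.1 intends to act on the results.

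**Conclusion.** The concern holds as a gap around a method the plan explicitly permits. Data-driven cutoffs are allowed for markers other than PD-L1 and the named TMB cutoff, followed by comparison with outcome, without a search range, selection adjustment or validation.

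Under an ordinary test at an assumed two-sided 5% level, the false-positive rate per unrelated marker is about 24%-43% for log-rank on PFS (central 50%-80% search, N = 23-27). It is about 10%-24% for Fisher on a binary outcome (central third to central 80%). The apparent effect is inflated. These figures rest on exponential PFS, the stated censoring and an exhaustive search. The direction does not depend on them: every searched setting at N = 23-27 exceeded 5%.

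The primary endpoint and its decision rule are untouched. The change is worth making, but it bears only on the exploratory results.

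**What to change.** In Section 11, keep published cutoffs for the other variables and replace the optimisation alternative with wording such as:

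> Markers without a published cutoff will be analysed as continuous variables, as for TMB. If a data-derived cutoff is shown, its p-value will be adjusted for the search (for example, by permutation of the maximally selected statistic over a prespecified range), and the cutoff and estimate will be labelled hypothesis-generating and unvalidated.

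The search range should be written down before outcomes are examined. Permutation of the maximum is one acceptable adjustment among several.

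The cost is one sentence and a few lines of code, with no extra patients, samples or procedures. The downside is that fewer exploratory associations will look significant.
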